**Figure 2. Hierarchical ranking for the primary endpoint**

= outpatient; = inpatient.

\* For participants enrolled as inpatients, inpatient mandatory data collection will occur until discharge or 30 days (whichever is shorter)

## 4. ADVERSE EVENTS

### 4.1. Adverse Event Reporting

Adverse events (AEs) will be captured in our data entry tool (RedCap). The DSMB will examine data periodically in order to compare the incidence of adverse events in both arms. Expedited reporting of individual AEs (within 48 hours of discovery by site investigators) will be required for severe AEs that are unexpected and felt to be probably or definitely associated with the study intervention. Such expedited reporting of AEs will be done from site investigators to the University of Pennsylvania study team, and the study team will in turn communicate these to the DSMB.

### 4.2. Key definitions

An AE is any untoward medical occurrence associated with the use of a drug in a study participant whether or not considered drug or biologic related. An AE can therefore be any unfavorable and unintended sign, symptom or disease temporally associated with the use of the pharmaceutical product.

### 4.3. Classification of AEs

A medically-qualified investigator will assess AEs in terms of causal relationship to intervention, seriousness, and expectedness using the following guidelines:

---

#### Classification of Adverse Events for Causal Relationship to the Study Intervention

---

Not related or unlikely related	There is not a reasonable causal relationship to the investigational product and the adverse event, or there is a low likelihood that a causal relationship exists.
Probably or definitely related	There is reasonable or definite evidence to suggest a causal relationship between the drug and adverse event.

---

The events will be classified as serious or non-serious adverse events:

*Serious Adverse Events (SAE)* are adverse events, in which the investigator or sponsor believe that any of the following outcomes occur:

- Death
- Life-threatening AE: Places the participant at immediate risk of death at the time of the event as it occurred. It does not include an AE that, had it occurred in a more severe form, might have caused death.
- Persistent or significant incapacity or substantial disruption of the ability to conduct normal life functions.
- Inpatient hospitalization or prolongation of hospitalization.
- Important medical events that may not result in death, be life threatening, or require hospitalization may be considered a serious adverse event when, based upon appropriate medical judgment, they may jeopardize the participant and may require medical or surgical intervention to prevent one of the outcomes listed in this definition above.

Expectedness: Expected AEs will be those that are reported to be associated with COVID-19.

The following AEs are expected, disease-related events in patients with COVID-19

1. Arrhythmias, including ventricular arrhythmias and atrial fibrillation.

2. Acute coronary syndromes with or without coronary stenoses on coronary angiography
3. Myocarditis or worsening cardiac function.
4. Shortness of breath, pneumonia, acute respiratory distress syndrome and respiratory failure.
5. Fever, malaise and myalgia.
6. Worsening cognitive function.
7. Limb ischemia, coagulopathy, thrombosis, embolus.
8. Hypotension or hypertension.
9. Diarrhea, nausea, or vomiting.
10. Anosmia (loss of sense of smell).
11. Leukopenia or leukocytosis, thrombocytopenia.
12. Worsening renal function (resulting in various electrolyte abnormalities).
13. Worsening liver function.
14. Death.

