### **8.2. Risks to study subjects**

All subjects will be adults able to give informed consent. Subjects will be enrolled regardless of sex, race or ethnicity, aiming to assure adequate representation of women and ethnic minorities. Children will not be enrolled.

The risks to study subjects are related to the potential side effects of the study intervention. The dose used in this trial is the starting dose for primary hypercholesterolemia and mixed dyslipidemia and is utilized as a chronic therapy, for months or years. We propose to administer this dose for only 10 days.

With chronic therapy, adverse reactions > 2% and at least 1% greater than placebo include abnormal liver blood tests (increased AST and ALT) increased creatine kinase (CPK), and rhinitis. Rhabdomyolysis have been reported in patients taking fenofibrate, but is considered extremely

rare, with <20 cases reported worldwide for fibrate monotherapy. Moreover, the median duration of therapy prior to rhabdomyolysis was 17.5 days. In the Fenofibrate Intervention and Event Lowering in Diabetes (FIELD) trial, 9,795 were randomized to fenofibrate or placebo for 5 years. This provided >8 million patient-days of observation in the active arm alone. In this trial, only 3 patients allocated to fenofibrate had rhabdomyolysis, which in each case fully resolved; this incidence was not significantly different than that of the placebo arm (1 case of rhabdomyolysis). The risk of rhabdomyolysis may be increased during co-administration with a statin, in renal failure, or hypothyroidism. Accordingly, we will exclude all patients with advanced renal dysfunction and those with a history of hypothyroidism.

Regarding statins, although there is an increase in reports of rhabdomyolysis with statin-fibrate combined therapy, this risk appears to be much higher when statins are combined with gemfibrozil than fenofibrate. In a meta-analysis of 6 trials including 1,628 subjects taking fenofibrate in combination with statin therapy, no case of myopathy or rhabdomyolysis was reported. This included data from the LCP-AtorFen trial, in which atorvastatin (40 mg/d) was administered alone or with fenofibrate for 12 weeks, as well as some studies with simvastatin (20 mg/d).

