### **Safety Analysis**

All subjects in the study at will be included in the safety analysis. The frequencies of adverse event (AE) by type, body system, severity and relationship to study drug will be summarized. Serious adverse events (SAE), if any, will be described in detail. AE incidence will be summarized along with the corresponding exact binomial 95% two-sided confidence intervals.

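### Expectedness is judged against COVID-19, not the drug, so a death, liver failure or renal failure attributed to study drug falls outside the 48-hour reporting rule

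*Protocol*

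**What the plan says.** Protocol section 4.1 gives sites 48 hours from discovery to report individual events to the coordinating study team, which passes them to the DSMB. The duty covers only "severe AEs that are unexpected and felt to be probably or definitely associated with the study intervention".

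Section 4.3 asks a medically qualified investigator to assess causality, seriousness and expectedness. For expectedness the only standard is "Expected AEs will be those that are reported to be associated with COVID-19". The 14-item list that follows includes "13. Worsening liver function", worsening renal function (item 12), low or high white-cell counts and low platelets (item 11), and death (item 14). No drug label or other reference safety information is named for this judgement. Section 4.3 classifies events as serious or non-serious and defines serious. It defines no severity grade.

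Elsewhere the protocol treats several of the same organ systems as drug concerns. Section 8.2 gives as adverse reactions of chronic therapy "abnormal liver blood tests (increased AST and ALT) increased creatine kinase (CPK), and rhinitis", and adds possible rises in creatinine and changes in blood counts. Section 2.7 stops study medication for, among other things, liver failure, a set rise in transaminases, and acute kidney injury below a set eGFR.

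Section 8.2 also has a separate rule for rhabdomyolysis: every case goes to the Principal Investigator and from there at once to the DSMB. The SAP (Safety Analysis) plans tables in which "severity and relationship to study drug will be summarized".

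**The concern.** Expedited reporting exists to bring a single, possibly drug-caused case to the people who can act on it before it is lost in group totals. Here expectedness answers a different question: whether the disease could produce the event. In this population the answer is yes for most organ failures and for death. The causality judgement then has no effect for those events, because an event judged definitely drug-related is exempt if it is also a known feature of COVID-19.

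At stake is how soon the DSMB learns of individual cases. When disease-related liver, renal and fatal events are common, a few drug-caused ones are hard to see in a comparison of rates by arm. Section 8.2 also says that periodic laboratory monitoring is not needed for so short a course, which gives individual reports more weight. The wording of the trigger adds a second difficulty: a site cannot apply severe consistently when the protocol defines only serious.

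**Working it through.** No calculation applies and the plan gives no figure to reproduce. The check takes the three joint conditions in section 4.1, assumes that the event is severe and judged probably or definitely related, and asks whether the section 4.3 list leaves it unexpected.

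| Event attributed to study drug | On the section 4.3 list? | Meets the section 4.1 rule? | Drug concern elsewhere in the protocol? |
|---|---|---|---|
| Death | Yes, item 14 | No | Not named as a fenofibrate effect in 8.2 |
| Liver failure | Yes, within item 13 | No | 2.7 (stops study drug); 8.2 (transaminases) |
| Renal failure | Yes, within item 12 | No | 2.7 (stops study drug); 8.2 (creatinine) |
| Marked fall in white cells or platelets | Yes, item 11 | No | 8.2 (blood counts) |
| Rhabdomyolysis | No | Yes, if the site treats it as unexpected | 2.7 and 8.2, with its own immediate route |

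The liver and renal rows take organ failure as the extreme of worsening function, which is the literal reading because the list sets no upper grade.

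The next step is to look for another route to the DSMB for the first four rows.

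1. Section 4.1: the DSMB compares adverse-event incidence between arms periodically. This does not depend on expectedness, but it is neither case-level nor expedited.
2. Section 6: the DSMB sets its own calls and reports and may ask for more data. The one milestone named is 50% of enrolment, 0.5 × 700 = 350 participants, and the DSMB may adapt it.
3. Section 2.7: stopping study medication protects the participant concerned, but it sends no report to the DSMB.
4. Section 8.2: the immediate route covers rhabdomyolysis only.
5. Sections 9 and 10: sites must follow national and institutional rules, and the DSMB has a charter. Neither section changes the definition in 4.3.

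On the trigger word, section 4.1 uses severe, section 4.3 defines serious, and the SAP tabulates severity. The visible text of the two documents contains no severity scale. The two words select different events: a hospitalisation of moderate intensity is serious but not severe, and an intense symptom may be severe but not serious.

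**The case against.** The strongest reply is that little is lost. All these events are captured as adverse events and compared by arm. The DSMB can meet when it chooses and request data. Deaths belong to the first tier of the primary endpoint and are followed closely. Study drug is stopped for the main liver and kidney events whatever their expectedness. Country-specific rules may add reporting duties that the visible text does not show. All of this stands, and it limits the gap to expedited reporting of individual cases. None of it changes the 48-hour rule.

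A second reply is that a label-based standard would change less than it seems to. The protocol itself describes raised transaminases, creatinine and CPK as drug effects, so routine rises would probably remain expected. That is correct. The gain lies in related deaths, organ failure and other events beyond what the label describes. Section 8.2 calls the creatinine rise mild and fully reversible, for example, so renal failure would exceed that description. A drug-based standard could also turn rhabdomyolysis, a reported drug reaction, into an expected event and remove it from the section 4.1 rule. The fix has to guard against this.

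Three stronger readings are tempting, and the documents do not support them.

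- A reader might infer that muscle harm is exempt too, because item 5 is "5. Fever, malaise and myalgia". Only myalgia is listed. Rhabdomyolysis, myopathy and raised CPK are not, and rhabdomyolysis has its own route.
- A reader might apply the death rates assumed in section 7.1 to 700 participants and call the result the number of lost reports. Those rates are all-cause and cover both arms. The rule matters only for deaths judged related, for which the documents give no estimate. A fatal event of an unlisted type might also still be expedited under its own term.
- A reader might infer that the DSMB sees these cases only in aggregate tables at mid-enrolment. Section 6 gives it wider powers than that.

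**Conclusion.** The point holds for death, liver failure, renal failure and blood-count changes attributed to study drug: followed as written, sections 4.1 and 4.3 together place them outside 48-hour reporting. They reach the DSMB through its periodic or requested reviews. For liver and kidney events this sits badly with sections 2.7 and 8.2, which treat them as drug concerns. The severe/serious mismatch is a separate, smaller defect in the same rule.

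The size cannot be put as a number of cases. It is a gap in one safety channel and does not affect adverse-event capture, randomization or the primary analysis. The conclusion rests on a literal reading of the list. It also assumes that nothing unseen overrides the main protocol: only the US part of Appendix 3 is visible, and the DSMB charter, the case report forms and the labels are not available. Severity grades could be in the case report forms.

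**What to change.** In Protocol section 4.3, judge expectedness against the reference safety information (the approved label) of the fenofibrate or fenofibric acid preparation used, and say that the nature and severity of the event count. A related fatal event or organ failure is then not expected merely because COVID-19 can cause it. Keep the COVID-19 list under a separate name, as disease-related events for aggregate review by arm.

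In section 4.1, replace severe with serious, so that the trigger uses the defined term. State in section 4.1 or 8.2 that the immediate rhabdomyolysis route applies regardless of expectedness. If the SAP keeps its tables by severity, name the scale.

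The cost is an amendment and a notice to sites. There would be somewhat more expedited reports, limited to events judged probably or definitely related.

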#### **4.4. Pregnancy:**

Limited available data of fenofibrate use in pregnant women are insufficient to determine any association between fenofibrate and the risk of major birth defects, miscarriage or adverse maternal or fetal outcomes. In animal reproduction studies, no evidence of embryo-fetal toxicity was observed with oral administration of fenofibrate in rats and rabbits during organogenesis at doses less than or equivalent to the dose used in this trial, based on body surface area (mg/m^2). Known pregnancy will be an exclusion criterion for enrollment. In addition, sexually active females of reproductive age who are not receiving active contraception will undergo a pregnancy test prior to randomized drug initiation. A positive test will prompt exclusion and/or discontinuation from the study. Additional processes related to pregnancy risks may be implemented in specific countries, to meet national regulatory requirements.

### **5. DATA COLLECTION**

The data coordinating center (DCC) will be established under the direction of [name]. The DCC will oversee randomization, data entry, and DSMB meetings. The data for this trial will be collected in *ad hoc* source electronic case report forms. All source documents collected in this trial will be housed by the site principal investigators.

Data capture and storage will be accomplished within the framework of the Research Electronic Data Capture (REDCap) project. REDCap is a secure, web-based application designed exclusively to support data capture for research studies. It provides an intuitive interface for data entry with data validation, audit trails for tracking data manipulation and export procedures, automated export procedures for seamless data downloads to common statistical packages, including SAS and STATA, and procedures for importing data from external sources.

All electronic data at the DCC will be housed in a secure server at the University of Pennsylvania. This will allow efficient workflows regardless of location, quarantine, and social distance policies, since investigators and research staff can access these documents using existing secure VPN mechanisms.

### **6. DATA SAFETY MONITORING BOARD**

A DSMB will be assembled to provide independent oversight of the project. The DSMB will be responsible for assessing: 1) baseline comparability between groups; 2) participant accrual rate and retention; 3) data quality with special emphasis on eligibility data; and 4) participant safety. The board will make recommendations regarding: study continuation, protocol modification, and

review of additional data. The conference call meetings and progress reports will be set by the DSMB. The DSMB will review detailed safety data according to pre-defined milestones (i.e., after 50% of participants are enrolled) which can be adapted as the trial proceeds, as per DSMB member decision.

## 7. STATISTICAL CONSIDERATIONS

### 7.1. Power calculations

We will enroll 700 participants. Participants will be randomized to one of 2 interventions (fenofibrate plus usual care vs. placebo plus usual care). Assuming feasible distributions of participants across each of the five hierarchies from the available published evidence, we performed 10,000 simulations of rank distributions of 700 participants, and determined that there will be 80% power at an alpha of 0.0492 (allowing for one interim analysis at 50% of enrollment with an alpha of 0.0054) to observe an 11% difference in median rank scores between the treatment arms. Power calculations were performed using python and PASS16.

Enrollment of 700 participants will increase our power for secondary outcomes. For the secondary outcome of number of days alive, out of the intensive care unit, free of mechanical ventilation (invasive and non-invasive), extracorporeal membrane oxygenation (ECMO) or maximal available respiratory support in the 30 days following randomization, assuming a standard deviation of 7 (the SD from the REPLACE COVID trial for this outcome), a sample size of 700 would have 90% power to estimate a 1.7 day mean difference between treatment arms. Assuming that the SD may be higher in the current study with the inclusion of outpatients, we would have a sufficient power to estimate a 3.4 day mean difference between treatment arms with a SD of 14.

For the secondary outcome of the WHO ordinal scale, based on the ordinal scale distributions from the Remdesivir trial, we would have 90% power to observe an OR of 1.5 for clinical improvement in the ordinal scale. Given the expected lower severity of illness in our participants, with an adjusted reasonable distribution towards the lower end of the scale, we would have 90% power to observe an OR of 1.7.

For the exploratory outcome of all-cause death, assuming a death rate of 14% (observed in REPLACE COVID), we would have sufficient statistical power to detect a HR of 1.4. Considering the mixed inclusion of inpatients and outpatients, if the death rate is 5%, we would have sufficient statistical power to detect a HR of 1.7.

For the exploratory outcome of number of days alive and out of the hospital, assuming a standard deviation of 8 (the SD from the REPLACE COVID trial for this unpublished outcome), a sample size of 700 would have 90% power to estimate a 2 day mean difference between treatment arms. Assuming that the SD may be higher in the current study with the inclusion of outpatients, we would have a sufficient power to estimate a 3.9 day mean difference between treatment arms with a SD of 16.

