### 7.2. Data Analysis Plan

The sample, both the baseline characteristics and the outcomes, will be explored and described using graphical techniques and summary statistics (means, medians, proportions and measures of variability) as appropriate. The initial description will consider the sample as a whole as well as by treatment arm.

The primary outcome variable will be the global rank score, as used previously in several similar randomized controlled trials to facilitate evaluation of composite outcomes of binary and continuous findings accounting for censorship for death. The predictor of interest for all outcomes will be randomized intervention (fenofibrate vs. control), with analyses based upon the total number of randomized participants. Initial descriptive estimates of all measures will be generated for study participants by treatment group. Statistics will include estimates of central tendency, measures of variability, and derived moments of skewness and kurtosis. Analyses of distributional properties will be performed to determine if variance stabilizing or normalizing transformations should be applied. Outliers will be assessed via visual inspection of distributions and checked for accuracy. Additionally, the intervention groups will be compared using Fisher's Exact tests.

The primary and secondary outcomes will be analyzed using a two-sided Wilcoxon rank sum test. Estimation, and 95% confidence intervals, of the differences between arms will be based on the Hodges-Lehman median difference as well as the Mann-Whitney Parameter, the probability that a subject from the fenofibrate arm has a score greater or equal to that of a subject for the control. This will be followed by a more comprehensive linear regression analysis allowing for assessments of the treatment effect on each continuous outcome of interest while controlling for effects of covariates including age, sex, inpatient vs. outpatient status at enrollment,  $\text{FiO}_2/\text{SpO}_2$  at the time of enrollment, ethnicity, body mass index, altitude above sea level and history of diabetes at baseline.

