Sequential monitoring and early stopping: Incidence rates of outcomes will be monitored throughout the trial and used for an interim analysis of efficacy and futility at 50% of enrollment. Group sequential methods for event rates will be used to control the Type I error to be 0.05 across repeated analyses. Critical values for interim testing will be defined based on an O'Brien-Fleming type bound (alpha 0.0052). With this approach, the interim test is conservative and the reduction in the overall power of the trial caused by interim testing is small. If needed, conditional power calculations will be used to assess the futility of continuation in the presence of a negative treatment effect. The DSMB will review data on adverse events and other safety issues to make an overall recommendation concerning the safety of continuing the trial.

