### FEnofibRate as a Metabolic INtervention for Coronavirus Disease 2019 (COVID-19): A randomized controlled trial (FERMIN trial)

April 6, 2022

This document details the statistical analysis plan in detail, including analyses that were pre-specified prior to data locking and unblinding. The document follows the original protocol analysis plan, but includes more methodologic detail and additional pre-specified analyses that are based on data not available at the time the protocol was written. These include: (1) A stratified analysis according to the specific fenofibrate/fenofibric acid preparation used, given recent data suggesting that there may be differential potency of fenofibrate as opposed to fenofibric acid *in vitro*, at least in some viral strains and/or culture systems; (2) Stratified analysis suggested by the trial DSMB during the course of the study, such as according to country, baseline disease severity, and COVID-19 pandemic epochs in which specific strains predominated.

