### Descriptive Statistics (Intention to treat cohort)

Analyses will be for the overall cohort, stratified by arm and stratified by in/out patient status at randomization. The outcomes and baseline characteristics of the subjects will be described using proportions for categorical variables and means/medians as well as standard deviations (SD) and interquartile range (IQR) for continuous variables.

**Primary Analysis:** This analysis will use a two-sided van Elteren test, the stratified version of the Wilcoxon rank sum test. For each stratum, estimation, and 95% confidence intervals of differences between arms will use both the Hodges-Lehman median difference and the Mann-Whitney Parameter, the probability that a subject from the treatment arm has a score greater or equal to that of a subject for the control. In addition to the primary outcome, the Wilcoxon test will be used to test hypotheses involving the continuous secondary and exploratory outcomes.

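### Protocol 7.1 and 7.2 give different alphas for the same interim look (0.0054 and 0.0052); with the only printed final level, 0.0492, either totals about 0.051 rather than 0.05.

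*Protocol*

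**What the plan says.** Protocol 7.1 powers the primary comparison of 700 participants "at an alpha of 0.0492 (allowing for one interim analysis at 50% of enrollment with an alpha of 0.0054". The 0.0492 appears there as the alpha of the power calculation, and no other final level is printed in either document.

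Protocol 7.2, in its paragraph on sequential monitoring, describes the same single look at half of enrollment. It bases the critical value on an O'Brien-Fleming "type bound (alpha 0.0052") and states no final level. The same paragraph promises: "Group sequential methods for event rates will be used to control the Type I error to be 0.05 across repeated analyses".

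The primary analysis is not an event-rate comparison. Protocol 7.2 says "The primary and secondary outcomes will be analyzed using a two-sided Wilcoxon rank sum test", and the SAP, under Primary Analysis, says "This analysis will use a two-sided van Elteren test, the stratified version of the Wilcoxon rank sum test".

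The SAP introduces itself with "The document follows the original protocol analysis plan, but includes more methodologic detail", but contains no interim level, final level or boundary. Protocol section 10 refers to a DSMB charter for interim recommendations; the charter is not among the documents.

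**The concern.** Two things look wrong. First, one look has two thresholds. The protocol's version log confirms that only one interim analysis is planned, so 0.0054 and 0.0052 cannot belong to different looks. An interim p-value between them crosses the bound in 7.1 but not the one in 7.2.

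Second, an O'Brien-Fleming interim level near 0.005 at half the information costs more of the 0.05 than a final level of 0.0492 allows for. If 0.0492 is applied at the end, a final p-value between 0.0480 and 0.0492 would be declared significant, although it fails a two-look O'Brien-Fleming design that holds 0.05.

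The reference to event rates adds to the doubt, because it leaves unclear which test statistic the bound governs.

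**Working it through.** **Inputs.** Interim alpha 0.0054 (Protocol 7.1) or 0.0052 (Protocol 7.2); final alpha 0.0492 (7.1); overall target 0.05 (7.2); two-sided tests (7.2 and SAP); one look at 50% of enrollment. Assumption: 50% of enrollment is taken as 50% of the information.

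**Formula.** With critical values c = z(1 − α/2) at each look, the overall two-sided error is

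1 − P(|Z1| < c1 and |Z2| < c2),

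where Z1 and Z2 are standard normal with correlation √0.5 = 0.7071. This allows for the overlap of data between the looks. Simply adding the alphas would give 0.0546 or 0.0544, which overstates the error.

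**Critical values.** z for 0.0054 is 2.7822; for 0.0052, 2.7944; for 0.0492, 1.9669; for 0.0480, 1.9774.

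**Overall error.**

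| Interim | Final | Overall two-sided error |
|---|---|---|
| 0.0054 | 0.0492 | 0.05129 |
| 0.0052 | 0.0492 | 0.05120 |
| 0.0052 | 0.0480 | 0.05002 |

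The promised 0.05 is not reproduced with either printed interim level. The excess is 0.0513 − 0.0500 = 0.0013, or 0.0512 − 0.0500 = 0.0012.

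**Which figure fits O'Brien-Fleming.** In the classic two-look form, the interim critical value is √2 times the final one. Solving for an overall 0.05 gives a final critical value of 1.9774, so the levels are 0.00517 and 0.04799. The 0.0052 of 7.2 is that interim level, rounded, and its partner rounds to 0.0480. The 7.1 pair has the right shape (2.7822 / 1.9669 = 1.4145, against √2 = 1.4142), but its constant is slightly too low, 1.967 rather than 1.977.

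**Other readings tried.**
- Final level needed for exactly 0.05: 0.0479 with interim 0.0054, and 0.0480 with interim 0.0052. To keep 0.0492, the interim level could be at most about 0.0026.
- O'Brien-Fleming-type alpha spending: 0.00557 and 0.0478 if 0.05 is spent two-sided; 0.00305 and 0.0490 if 0.025 is spent per side. Neither matches the printed figures.
- Levels read as one-sided: 0.0509 and 0.0508.
- Information fraction at the look (assumed range, not given in the documents): from 40% to 60%, the 7.1 pair totals 0.0520 to 0.0506, and 0.0052 with 0.0492 totals 0.0518 to 0.0506.

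**Effect on power.** Take the standardized effect that gives 80.0% at 0.0492: 1.9669 + 0.8416 = 2.8085. At 0.0480 the power is Φ(2.8085 − 1.9774) = Φ(0.8311) = 79.7%. To hold 80% at that level, N = 700 × [(1.9774 + 0.8416) / 2.8085]² = 705.3, so 706. These figures count the final test alone, as 7.1 states its power. Counting rejection at either look, power is 80.19% for 0.0054 with 0.0492 and 79.89% for 0.0052 with 0.0480; on that basis 702 participants would hold 80%.

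**The case against.** The strongest reply is that the discrepancy is trivial. The two interim levels differ by 0.0002. The chance of an interim p-value landing between them is 0.0002 under the null and about 0.35% at the effect giving 80% power. The excess error is little more than one part in a thousand. That is right about the size, and nothing here suggests the trial would be invalid.

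It can also be said that the overrun is conditional. The 0.0492 is printed only as the alpha of the power calculation, so 7.2 could be followed with 0.0052 and whatever final level meets 0.05. This stands as a qualification, but that final level is written nowhere, and a reader looking for one finds only 0.0492.

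The power loss should not be pressed. The stated 80% comes from 10,000 simulations, with a Monte Carlo standard error of √(0.8 × 0.2 / 10,000) = 0.4 points, larger than the 0.3-point fall. The 79.7% is therefore an approximation that shows the change is cheap, not a correction of the simulated figure.

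Three further defences do not remove the point. The DSMB charter may state a boundary, but it could not make two conflicting protocol values agree. A binding futility stop could lower the total error, but the futility check is to be done only if needed and has no stated boundary. The excess would vanish if the look came much later (the 7.1 pair totals 0.0495 at 80% information), but the look is set at half of enrollment.

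**Conclusion.** The concern holds. The protocol gives two alphas for its only interim look, and neither combines with the only printed final level to give 0.05. The overall two-sided error is 0.0513 or 0.0512, an excess of 0.0012 to 0.0013.

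The contradiction between 7.1 and 7.2 needs no calculation. The overrun rests on three assumptions: 0.0492 is the final threshold, half of enrollment is half of the information, and no binding futility rule applies. It persists for information fractions from 40% to 60%. Calling 0.0052 the matching level rests on the classic O'Brien-Fleming form at exactly half the information; O'Brien-Fleming-type spending gives other values, so the form has to be named.

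The effect is small, but an efficacy threshold should not contradict itself or miss its own stated error rate. It should be corrected.

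**What to change.** State one matched pair for the primary rank test, identically in Protocol 7.1, Protocol 7.2 and the SAP. One choice is interim 0.0052 and final 0.0480 (0.00517 and 0.04799 before rounding). The alternative is a named alpha-spending function with its exact form, and the final level computed from the information actually available at the interim. Replace the reference to event rates in 7.2 with the primary rank test, and restate the power in 7.1 at the chosen final level, ideally by rerunning the simulations (about 79.7% under the normal approximation).

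The cost is a few words in two protocol sections and one line in the SAP, with about 0.3 points of stated power at 700 participants. No change to enrollment, endpoints or conduct is needed. Under Protocol section 10 the protocol edits need ethics and regulatory approval, so they would sensibly go with the next amendment, and the SAP line can be written at once.
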